## **Summary**

Compared to healthy people without migraine, migraine is associated with alterations in brain structure and function. This is a prospective, longitudinal, open-label study that will investigate brain magnetic resonance imaging changes amongst individuals with migraine following treatment with erenumab.

The Specific Aims of this study are to:

- 1. Identify changes in brain function and structure that correlate with response to erenumab.**
- 2. Develop models using imaging data to predict which patients will respond to erenumab.**  
Pre-treatment and early post-treatment imaging data will be used separately for predictive modeling.

The study will include 50 subjects with migraine aged 18-65 years who have 6-25 migraine days per month at baseline. Following a 4-week run-in phase, subjects will be treated twice with once monthly subcutaneous injections of erenumab 140 mg. Questionnaires, structured interviews, cognitive tests, quantitative sensory testing and brain imaging will be performed prior to and following erenumab treatment. These data will be collected at early time points after the first treatment as well as at eight weeks following the first treatment to allow for identification of early and late effects of erenumab on clinical, physiologic, and imaging outcomes and to determine if early physiologic and imaging outcomes predict clinical outcomes at eight weeks. Physiologic and imaging data will be compared to already collected data from healthy controls so as to interpret changes that are seen following treatment with erenumab.

The primary hypothesis is that improvements in migraine patterns associated with erenumab treatment will be associated with “normalization” of brain function. Secondarily, it is hypothesized that improvements in migraine patterns associated with erenumab treatment will be associated with “normalization” of brain structure, pain thresholds, and cognitive performance. Finally, it is hypothesized that exploratory analyses will demonstrate that there are early changes in brain function following the first treatment with erenumab and that these early changes will be predictive of longer-term clinical responsiveness to erenumab.

## **Background**

Migraine is a highly prevalent disorder that affects 38 million people in the US and is associated with moderate to severe pain, hypersensitivities to sensory stimuli, nausea, vomiting, and reduced quality of life. (1-3) Annual costs from migraine are estimated at \$20 billion in the United States and €27 billion in Europe. (4, 5) Migraine remains poorly treated and there are currently few options for the preventive treatment of migraine. The release of erenumab to the market represents a substantial improvement in the landscape of migraine preventive treatment.

Phase 2 and 3 randomized, double-blind, placebo-controlled studies have demonstrated that erenumab is safe and effective for the prevention of episodic and chronic migraine. (6-8) Erenumab received US Food and Drug Administration approval for the prevention of migraine in May 2018. Structural and functional neuroimaging could provide important insights into central mechanisms of treatment response and imaging biomarkers that track treatment response or are indicators for early treatment response. A few studies have demonstrated normalization of functional activation patterns, reorganization of functional connectivity, and normalization of brain metabolism following migraine treatment with external trigeminal neurostimulation, topiramate, and precision ophthalmic tints. (9-12) However, the effects of erenumab on brain function and structure, including the processing of painful stimuli, have been inadequately investigated. Furthermore, it is possible that measures of brain function and structure could serve as predictors for clinical response to erenumab, either prior to treatment or early after the first treatment. It is of clinical interest to interrogate whether neuroimaging is a useful technique for establishing a brain biomarker for predicting treatment response and measuring treatment responses earlier than is possible using clinical measures alone.

This study will investigate longitudinal changes in brain structure and function in high frequency episodic migraine and chronic migraine patients who are responding to erenumab treatment compared to those patients who are non-responders. In addition, pre-treatment and early post-treatment brain imaging data will be used to build models that predict which individual migraine patients will respond to erenumab treatment.

[figure not shown]
The Specific Aims of this study are to:

- 1. Identify changes in brain function and structure that correlate with response to erenumab.** This objective of this aim is to investigate effects of treatment with erenumab on brain function and structure in patients who respond to treatment with erenumab and in patients who do not respond to treatment with erenumab.
- 2. Develop models to predict which patients will respond to erenumab.** The goal of this aim is to identify structural and functional brain magnetic resonance imaging predictors of response to erenumab in patients with migraine. Specifically, this aim seeks to identify those migraine patients who are going to have a positive response to erenumab treatment versus those who will not respond to treatment. Pre-treatment and early post-treatment imaging data will be used separately, and in combination, for predictive modeling.

[figure not shown]
## **Published Work and Preliminary Data**

Our team has performed multiple studies that are directly relevant to the goals of this project and serve as evidence of our ability to successfully conduct this study. We have completed studies comparing noxious heat-induced brain activation patterns in people with migraine vs. healthy controls. (13) These studies showed that migraineurs have greater pain-induced activation in several brain regions, many of which participate in cognitive aspects of pain processing. For several of these regions, the extent of greater activation correlated with the frequency of headaches, serving as strong evidence for a direct relationship between having migraine and greater activation of these pain-processing brain regions and at least suggesting that reductions in headache frequency would correlate with reductions in pain-induced activation. Our resting-state functional connectivity studies have investigated functional connectivity of affective-emotional pain processing regions and of descending pain modulatory brainstem regions. (14, 15) These studies demonstrated that migraineurs have atypical functional connectivity and the extent of atypical connectivity correlates with measures of migraine disease burden such as number of years with migraine and allodynia symptoms. Our structural MRI studies have shown migraineurs to have atypical structure of the brainstem and abnormal cortical thinning with age, aberrant correlations between brain cortical thickness and cutaneous pain thresholds, atypical cortical thickness correlations, and abnormal white matter tract integrity. (16-18) Furthermore, our work has shown migraineurs with interictal photosensitivity to have thicker cerebral cortex in parieto-occipital and fronto-parietal regions. (19) Finally, our machine-learning multivariate pattern analyses have yielded migraine classifiers that use brain structural data to differentiate the brain of an individual chronic migraineur from that of a healthy control (see Figure 1) or episodic migraineur (see Figure 2) with high accuracy (American Headache Society Wolff Award winning paper). (20) Our classifiers based on resting state functional connectivity data differentiate the brain of an individual migraineur from a healthy control with high accuracy (American Academy of Neurology Harold Wolff – John Graham Award winning research, see Figure 3). (20, 21) In addition, we developed a decision support system using multi-modality imaging data to interrogate the utility of combining structural and functional imaging data for migraine patient discrimination and the accuracy of such discrimination. (see Figure 4) (22) Results showed better classification accuracy when combining structural and functional data than using either data type alone.

[figure not shown]
**Figure 1:** Regions that allow for accurate discrimination of the chronic migraine brain from that of a healthy control. (20) Structural measures (i.e. cortical thickness, volume, surface area) of the colored brain regions allow for classification of the individual brain MRI as belonging to a person with chronic migraine vs. a healthy control with 86.3% average accuracy. Similar model-building techniques can be used to construct classifiers that predict response to erenumab.

[figure not shown]
**Figure 2:** Regions that allow for accurate discrimination of the chronic migraine brain from that of an episodic migraineur. (20) Structural measures (i.e. cortical thickness, volume, surface area) of the colored brain regions allow for classification of the individual brain MRI as belonging to a person with chronic migraine vs. episodic migraine with 84.2% average accuracy. Similar model-building techniques can be used to construct classifiers that predict response to erenumab.

**Figure 3:** Functional connectivity patterns for the left and right amygdala that contribute to the classification accuracy of distinguishing between individual migraine patients and individual healthy controls. (21) Whole-brain functional connectivity patterns of 6 regions distinguished migraine patients from healthy controls with a best classification accuracy of 86.1%. Migraineurs with longer disease durations were more accurately classified than migraine patients with shorter disease durations. Similar model building techniques could be used to track and predict response to erenumab treatment.

**Figure 4:** Key brain areas (based on brain structural imaging) and functional connections (based on resting-state imaging) that contribute to distinguishing migraine patients from healthy controls. (22) The combined model that included structural and functional data provided greater accuracy (83%) compared to the model based on structural data alone (80%) and the model built on functional connectivity data alone (75%). The combination of structural and functional brain imaging data may increase the classification accuracy for predicting/determining treatment response to erenumab.

## **Specific Aims**

- 1. Identify changes in brain function and structure that correlate with response to erenumab.** The objective of this aim is to investigate effects of treatment with erenumab on brain function and structure in patients who respond to treatment with erenumab and in patients who do not respond to treatment with erenumab. Specifically, this aim will assess changes in brain structure (cortical thickness, volume, area, white matter integrity), brain perfusion, resting-state functional connectivity, and pain-induced brain activation patterns in treatment responders and in treatment non-responders. This aim will identify structural and functional brain biomarkers for treatment response with erenumab.
- 2. Develop models to predict which patients will respond to erenumab.** The goal of this aim is to identify structural and functional brain magnetic resonance imaging predictors of response to erenumab in patients with migraine. Specifically, this aim seeks to identify those migraine patients who are going to have a positive response to erenumab treatment versus those who will not respond to treatment. Pre-treatment and early post-treatment imaging data will be used separately, and also in combination, for predictive modeling.

## **Methods**

**Study Design:** This is a prospective, open-label, longitudinal, pre- and post-treatment magnetic resonance imaging (MRI) study of patients treated with erenumab. A summary of the study flow is presented in Table 1.

**Table 1- Study Flow.**

	Run in Phase (time: -4 wks)	Baseline (time: 0)	First Follow-up (time: 2 wks)	Second Follow-up (time: 4 wks)	Third Follow-up (time: 8 wks)	Fourth Follow-up (time: 12 wks)
Determine Eligibility	X	X				
Questionnaires	X	X	X	X	X	X
QST		X	X		X	
MR Imaging		X	X		X	
Cognitive Testing		X	X		X	
Vital Signs		X	X	X	X	X
Urine Pregnancy Test		X		X		
Erenumab Treatment		X		X		
Headache Diary	X	X	X	X	X	X

**Participants:** Up to 67 adult patients who are at least 18 years of age but younger than 66 years of age with high frequency episodic migraine or chronic migraine with and/or without aura will be enrolled into the run-in phase of this study at Mayo Clinic Arizona. Enrollment will stop once 50 subjects provide headache diary during the run-in phase that meets eligibility criteria (i.e. documented 6-25 migraine days per 28 days). Previously collected data of healthy control subjects (n=50) will be used for data comparison. Exclusion and inclusion criteria will be modeled after those used in the phase 2 and 3 trials of erenumab for the prevention of migraine. (6, 8) In addition, patients who have contraindications to MRI (e.g. metal implants, aneurysm clips, severe claustrophobia) will be excluded from study participation. Potential participants will be excluded if they have active chronic pain conditions other than migraine (e.g. chronic pelvic pain) or acute pain conditions (e.g. recent surgery). Potential participants who have sensory disorders that might affect the perception of cutaneous thermal stimuli will also be excluded (e.g. peripheral neuropathy).

## **Subject Eligibility**

### *Inclusion Criteria*

- Adults 18-65 years of age

- Episodic migraine (with or without aura) or chronic migraine according to the diagnostic criteria included within the International Classification of Headache Disorders 3 (ICHD-3) (23)
  - Episodic Migraine
    - A. At least 5 attacks fulfilling criteria B-D
    - B. Headache attacks lasting 4-72 hours (when untreated or unsuccessfully treated)
    - C. Headache has at least two of the following four characteristics:
      - a. Unilateral location
      - b. Pulsating quality
      - c. Moderate or severe pain intensity
      - d. Aggravation or causing avoidance of routine physical activity
    - D. During headache at least one of the following:
      - a. Nausea and/or vomiting
      - b. Photophobia and phonophobia
    - E. Not better accounted for by another ICHD-3 diagnosis
  - Chronic Migraine
    - A. Headache (migraine-like or tension-type like) on at least 15 days per month for longer than 3 months, and fulfilling criteria B and C
    - B. Occurring in a patient who has had at least five attacks fulfilling criteria B-D for "episodic migraine" (above)
    - C. On at least 8 days per month for longer than 3 months, fulfilling any of the following:
      - a. Criteria C and D for migraine without aura
      - b. Criteria B and C for migraine with aura
      - c. Believed by the patient to be a migraine at onset and relieved by a triptan or ergot derivative
    - D. Not better accounted for by another ICHD-3 diagnosis
- 6-25 migraine days per month on average over the 3 months prior to screening, confirmed by run-in phase prospective data collection
- Duration since migraine onset of at least 12 months prior to screening based on medical records and/or patient self-report

#### *Exclusion Criteria*

- Older than 50 years of age at migraine onset
- History of cluster headache or hemiplegic migraine
- Continuous headache pain (i.e. no pain-free periods of any duration during the one month before screening)

- Opioid- or butalbital-containing analgesics on 6 or more days per month during the 2 months prior to the start of the baseline phase
- History of major psychiatric disorder such as schizophrenia and bipolar disorder
- History or evidence of any unstable or clinically significant medical condition, that in the opinion of the investigator, would pose a risk to subject safety or interfere with the study evaluation, procedures, or completion
- No therapeutic response in migraine prevention after an adequate therapeutic trial of 4 or more of the following medication categories:
  - Category 1: divalproex sodium, sodium valproate
  - Category 2: topiramate
  - Category 3: beta-blockers
  - Category 4: tricyclic antidepressants
  - Category 5: venlafaxine or desvenlafaxine, duloxetine or milnacipran
  - Category 6: flunarizine, verapamil
  - Category 7: lisinopril, candesartan
  - Category 8: botulinum toxin

No therapeutic response is defined as no reduction in headache frequency, duration, or severity after administration of the medication for at least 6 weeks at the generally accepted therapeutic dose(s) based on the investigator's assessment. Lack of sustained response to a medication and failure to tolerate a therapeutic dose are not considered to be "no therapeutic response".

- Concomitant use of 3 or more of the following medications for migraine prevention within 2 months before the start of the baseline phase or throughout the study: divalproex sodium, sodium valproate, topiramate, carbamazepine, gabapentin, beta-blockers, tricyclic antidepressants, venlafaxine, desvenlafaxine, duloxetine, milnacipran, flunarizine, verapamil, lomerizine, lisinopril, candesartan, clonidine, guanfacine, cyproheptadine, methysergide, pizotifen, butterbur, feverfew, magnesium (at least 600 mg per day), riboflavin (at least 100 mg per day).

Use of up to two medications is permitted as long as the dose has been stable for at least 2 months before the start of the run-in phase and during the study.

- Botulinum toxin (in the head and/or neck region) within 4 months before the start of the baseline phase and throughout the study
- Ergotamine derivatives, steroids, and triptans used for migraine **prophylaxis** within 2 months before the start of the baseline phase and throughout the study
- Procedures (e.g. nerve blocks) used for migraine prophylaxis within 2 months before the start of the baseline phase and throughout the study

- History of myocardial infarction, stroke, transient ischemic attack, unstable angina, coronary artery bypass surgery, or other revascularization procedures within 12 months prior to screening.
- Contraindications to MRI including, but not limited to:
  - Metal implants
  - Aneurysm clips
  - Severe claustrophobia
  - Implanted electronic devices
  - Insulin or infusion pump
  - Cochlear/otologic/ear implant
  - Non-removable prosthesis
  - Implanted shunts/catheters
  - Certain intrauterine devices
  - Tattooed makeup
  - Body piercings that cannot be removed
  - Metal fragments
  - Wire sutures or metal staples
- Factors that Reduce MR Image Quality and Interpretability
  - Dental braces or other non-removable devices (e.g. retainers)
  - Prior brain surgery
  - Known brain MRI abnormality that in the investigator's opinion will significantly impact MRI data
- Sensory disorders that in the investigator's opinion might affect perception of cutaneous thermal stimuli (e.g. peripheral neuropathy)
- Pregnancy
- Lactation
- Not willing to use a reliable form of contraception (for women of childbearing potential) through 16 weeks after the last dose of erenumab. Acceptable methods of birth control include not having intercourse, hormonal birth control methods, intrauterine devices, surgical contraceptive methods, or two barrier methods (each partner must use a barrier method) with spermicide. A reliable form of contraception must be started prior to or at the time of starting the run-in phase. Not being of childbearing potential is defined as any woman who:
  - Is post-menopausal by history, defined as:
    - At least 55 years of age with cessation of menses for 12 or more months, OR
    - Younger than 55 years of age but no spontaneous menses for at least 2 years, OR
    - Younger than 55 years of age and spontaneous menses within the past 1 year, but currently amenorrheic (e.g. spontaneous or secondary to hysterectomy),

AND with postmenopausal gonadotropin levels (luteinizing hormone and follicle-stimulating hormone levels at least 40 IU/L) or postmenopausal estradiol level (less than 5 ng/dL) or according to the definition of "postmenopausal range" for the laboratory involved.

OR

- Underwent bilateral oophorectomy OR
- Underwent hysterectomy OR
- Underwent bilateral salpingectomy

- Currently receiving treatment in another drug study or an investigational device study, or less than 90 days prior to screening since ending treatment on another investigational device or drug study(-ies)
- Has received CGRP monoclonal antibody within 4 months of the start of the run-in phase
- Active chronic pain condition that in the investigator's opinion is unrelated to migraine (e.g. chronic pelvic pain)
- Acute pain condition that in the investigator's opinion is unrelated to migraine (e.g. post-surgical pain)
- Unable to provide informed consent
- Less than 80% compliance with providing headache diary data during the run-in phase (i.e. provides data on less than 80% of days)

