classic imputation methods commonly used in clinical trials will be adopted.(6) Specifically, for months with 20-27 days of dairy data, the values for missing entries will be imputed by prorating scores of 28-day post-treatment periods. That is, monthly migraine frequency can be calculated as the ratio of number of observed migraine days to number of observed days multiplied by 28. For months with less than 10 days of dairy data, monthly migraine frequency will be estimated by the substitution of the patient's previous 28-day period score, multiplied by the ratio of the mean for all patients in the same period to the mean for all patients in the previous period. For post-treatment periods with 10-19 days of diary data, scores will be estimated using a mean of both methods.

**Follow up visits One through Four (see table 1):** Four follow-up visits will be scheduled: at weeks 2, 4, 8 and 12 post-initial treatment with erenumab (week 2 = 14 days +/- 2 days since first visit; week 4 = 28 days +3 days since first visit; week 8 = 56 days +/- 3 days since first visit; week 12 = 84 days +/- 5 days since first visit). The early follow-up at 2 weeks will be utilized for repeat QST, brain imaging and cognitive testing so that data are available for investigating early markers/predictors of treatment response. A second treatment with erenumab will occur during the 4-week visit. Imaging, QST and neurocognitive testing will be repeated during the 8-week visit, allowing for determination of biomarkers for treatment response that might not have been found at the early time-point of 2 weeks and that can be correlated with clinical measures of treatment response (i.e. changes in migraine day frequency). The 12-week visit will allow for further assessment of safety and efficacy.

**Acute Migraine Therapy:** Patients will be allowed to use acute headache treatments including migraine-specific medication (e.g. triptans, ergotamine derivatives) and NSAIDs during the study.

**Other Migraine Preventive Therapy:** Patients will be allowed to use two or fewer migraine preventive therapies in addition to erenumab as long as the dose has been stable for at least 2 months before the start of the run-in phase. Changes to the dose of such treatments will not be allowed during this study unless necessary due to safety issues or lack of tolerability.

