### *Definition of Serious Adverse Events*

A serious adverse event is defined as an adverse event that meets at least 1 of the following serious criteria:

- fatal
- life threatening (places the subject at immediate risk of death)
- requires in-patient hospitalization or prolongation of existing hospitalization
- results in persistent or significant disability/incapacity
- congenital anomaly/birth defect
- other medically important serious event

An adverse event would meet the criterion of “requires hospitalization,” if the event necessitated an admission to a health care facility (e.g., overnight stay). If an investigator considers an event to be clinically important, but it does not meet any of the serious criteria, the event could be classified as a serious adverse event under the criterion of “other medically important serious event.” Examples of such events could include allergic bronchospasm, hypersensitivity reaction, or events that necessitate an urgent intervention.

*Reporting Procedures for Adverse Events That do not Meet Serious Criteria*

The investigator is responsible for ensuring that all adverse events observed by the investigator or reported by the subject that occur after the dose of investigational product through the end of the safety follow-up visit (8 weeks after the last dose of investigational product) are reported using the Adverse Event case report form. The Adverse Event case report form is included within the Appendix of this protocol.

The investigator must assign the following adverse event attributes:

- adverse event diagnosis or syndrome(s), if known (if not known, signs or symptoms)
- dates of onset and resolution (if resolved)
- intensity
- outcome
- action taken
- assessment of relatedness to investigational product

Assessment of whether the adverse event is possibly related to the investigational product is indicated by a “yes” or “no” response to the question: “Is there a reasonable possibility that the event may have been caused by the investigational product?”

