The Adverse Event case report form will be completed by the member of the research team that receives the information from the participant about the adverse event. The Principal Investigator will always be responsible for initially and dating the form, indicating that the Principal Investigator has reviewed the adverse event with the research team member, determining the relationship of the adverse event to the study, and determining if the adverse event meets criteria for a serious adverse event.

*Reporting Procedures for Serious Adverse Events*

The investigator is responsible for ensuring that all serious adverse events observed by the investigator or reported by the subject that occur after signing of the informed consent through the end of the safety follow-up visit (8 weeks after the last dose of investigational product) are recorded in the subject’s record and to the local Institutional Review Board according to that Board’s policy.

Reporting of adverse events to Amgen will occur in accordance with the “Safety Data Exchange Requirements” as provided by Amgen. These requirements dictate the need for and timing of reporting adverse events to Amgen. A copy of the “Safety Data Exchange Requirements” has been included within the Appendix of this protocol.

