#### *Protection Against Risks:*

Individuals who are known to be pregnant or lactating will be excluded from study participation. Women of childbearing potential who are not known to be pregnant will have urine pregnancy testing before the 4 week run-in phase and prior to each of the two erenumab treatments. Women found to be pregnant will not receive any additional treatments with erenumab. Women of childbearing potential will be required to use a reliable form of contraception from the start of the run-in phase through 16 weeks after the last dose of erenumab (details provided in 'eligibility criteria' section of this protocol).

Measures that will be taken to protect PHI: All information collected from study participants will be locked in a secure location. Identifying information will be removed from the data forms and replaced by unidentifiable codes. Electronic databases/spreadsheets will be password protected and only accessible to those with access rights. Data will be entered into REDCap. (43) REDCap is a secure web-based application used for designing and managing clinical research databases. REDCap's design addresses the National Center for Research Resources statement that the future of biomedical research will involve collaborations amongst many scientists in different locations linked by high-speed computer networks thus enabling data submission, data sharing and data analyses. (43, 44) REDCap is accessible to study investigators via any computer with a Web browser. Once data are entered into data collection forms, data automatically upload to the registry data file. The registry complies with all HIPAA regulations, requires a log-in ID and password, and users only have access to specific functions (e.g. view data, add data, change data, etc.) once granted rights for those specific functions. Data can be exported into numerous formats utilized by several frequently used statistical packages including SPSS, SAS, R, Excel, Stata and others.

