## **ISS – Timeframes for Submission of Safety Data to Amgen**

### **For Interventional studies with Amgen IMP\*:**

Safety Data	Timeframe for Submission to Amgen
Suspected Unexpected Serious Adverse Reaction (SUSARs)	Sent to Amgen at time of regulatory submission
Serious Adverse Events (SAEs)	Not required, unless contractually specified per study
Adverse Events not meeting serious criteria	Not required, unless contractually specified per study
Events of Interest	Not required, unless contractually specified per study
Pregnancy/Lactation	Within 10 calendar days of Sponsor awareness
Event listing for reconciliation	As specified per contract

\*Specific requirements are to be outlined in the Research Agreement

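### The safety windows close about 8 weeks before the required contraception period ends, and the SAE cut-off leaves the birth-defect criterion almost impossible to meet

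*Combined protocol and SAP*

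**What the plan says.** - **Contraception.** The Exclusion Criteria list as a ground for exclusion: "Not willing to use a reliable form of contraception (for women of childbearing potential) through 16 weeks after the last dose of erenumab". Protection Against Risks repeats the period and starts it at run-in. Possible Risks says that the risks in pregnancy and lactation are not established.
- **Serious criteria.** Definition of Serious Adverse Events includes "congenital anomaly/birth defect".
- **Collection windows.** SAEs are those "that occur after signing of the informed consent through the end of the safety follow-up visit (8 weeks after the last dose" of product). Non-serious events have the same end point, but their collection starts after dosing.
- **Visits.** The second and last dose is given at the week-4 visit. The final visit is timed from the first treatment visit: "week 12 = 84 days +/- 5 days since first visit". No later contact is scheduled, and the diary also runs 12 weeks.
- **Pregnancy tests.** Under Protection Against Risks, women of childbearing potential "will have urine pregnancy testing before the 4 week run-in phase and prior to each of the two erenumab treatments". In Table 1 the "Urine Pregnancy Test" row is marked only at baseline and week 4. The Run in Phase section allows the initial visit to be held by telephone.
- **A positive test.** The only stated consequence is that no more erenumab is given. Follow-up of the pregnancy is not described.
- **Manufacturer reporting.** The safety-data appendix requires pregnancy and lactation reports "Within 10 calendar days of Sponsor awareness", with no end date, and leaves specific requirements to a Research Agreement.

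**The concern.** The protocol gives contraception as a protection against a risk it calls unestablished, and it asks for that protection for twice as long after the last dose as it collects adverse events. A pregnancy that begins or is recognised between the last visit and the end of the contraception period would reach the study only if the participant volunteered it.

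The birth-defect criterion is the sharper problem. It is listed as a reason to call an event serious, but the rule on which serious events are recorded closes long before a term birth could follow conception on study. Site staff who apply the cut-off literally would not record a congenital anomaly reported later, although it meets the protocol's own definition.

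The pre-run-in pregnancy test is a plain contradiction: one section promises it, the schedule omits it, and the visit at which it would naturally be done may be a telephone call.

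**Working it through.** All days are counted from the baseline (first treatment) visit, day 0.

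**The plan's own figure.** Last dose at day 28 plus 8 weeks (56 days) gives day 84, the week-12 visit. The stated 8-week safety follow-up is therefore reproduced at nominal timing.

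**Gap between contraception and collection**

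| Input | Source | Value |
|---|---|---|
| Second dose | Follow up visits One through Four (28 days, +3) | day 28 to 31 |
| Contraception period | Exclusion Criteria; Protection Against Risks | 16 × 7 = 112 days |
| Last visit, end of AE/SAE collection | Follow up visits One through Four; SAE reporting section | day 84, range 79 to 89 |

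1. Contraception ends on day 28 + 112 = 140 to day 31 + 112 = 143.
2. The nominal gap is 140 − 84 = 56 days.
3. The shortest gap is 140 − 89 = 51 days, and 51/112 = 46% of the contraception period.
4. The longest gap is 143 − 79 = 64 days, and 64/112 = 57%.
5. The week-4 window is printed as +3 days only. If ±3 was meant, the earliest second dose is day 25, contraception then ends on day 137, and the shortest gap is 137 − 89 = 48 days. The range becomes 48 to 64 days and the conclusion is the same.

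**Pregnancy tests.** The last scheduled test is at week 4, before the second dose. None is scheduled in the 112 days after that dose, although the week-8 and week-12 visits fall within them.

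**Birth-defect criterion against the SAE window.** The documents give no gestation length, so I assume 38 to 40 weeks, or 266 to 280 days.

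1. Conception on day 0 gives a term birth on day 266 to 280.
2. The SAE window closes on day 89 at the latest, so the birth falls at least 266 − 89 = 177 days and up to 280 − 89 = 191 days after that latest closing date.
3. Counting from the start of run-in (28 ± 3 days before baseline) adds at most 31 days: 31 + 89 = 120 days, still well short of 266.

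No term birth after on-study conception can fall inside the window. A prenatal diagnosis before week 12 remains possible, so the right description is almost never, not never.

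**Pre-run-in test, side by side**

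| Place | Test before run-in? |
|---|---|
| Protection Against Risks | Yes |
| Table 1 | Not marked; baseline and week 4 only |
| Run in Phase | Initial visit may be by telephone; no test mentioned |

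**The case against.** A contraception rule is precautionary and an AE window concerns data collection, so differing lengths are not in themselves a contradiction. That is fair. It also limits several stronger conclusions that a reader might draw:

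- **That all safety collection stops at 8 weeks.** It does not. The AE and SAE windows close, but the duty to report pregnancy to the manufacturer has no end date.
- **That this duty cannot be met.** It arises on awareness. A pregnancy that is reported can be passed on at any date, and one that nobody reports triggers no duty. The fair point is that no active route to awareness after week 12 is described.
- **That the protocol defines a 16-week exposure period.** It states a contraception requirement of that length. Treating it as the at-risk period is an inference.
- **That the safety report would claim no pregnancies.** The Safety Analysis promises descriptive AE proportions and makes no statement about pregnancies.
- **That nothing could come to light in the 112 days after the last dose.** Visits with AE review take place at weeks 8 and 12, and the on-study tests are tied to dosing decisions.
- **That the safety visit breaches its own timing.** It can fall 79 − 31 = 48 to 89 − 28 = 61 days after the last dose, so up to 8 days short of 56. That is ordinary visit-window slack, and collection runs to the visit itself.

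Two further limits stand. The consent form and the Research Agreement were not available and may contain instructions on reporting pregnancy. The missing pre-run-in test has limited consequence, because a test before the first dose is planned at baseline in every relevant section.

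None of this answers the two remaining points: the SAE cut-off as written defeats a listed serious criterion, and the sections disagree on the pre-run-in test.

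**Conclusion.** The point holds within those limits. For about 8 weeks (51 to 64 days on the printed windows) contraception is still required while no visit, pregnancy test or AE/SAE collection is scheduled. On an assumed gestation of 38 to 40 weeks, the SAE cut-off excludes any term birth after on-study conception, so the birth-defect criterion could almost never be met as written. The supplied text describes neither an active way to learn of a pregnancy after week 12 nor follow-up of an exposed pregnancy. The statement on the pre-run-in test is contradicted by Table 1 and hard to square with a telephone visit.

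The practical scale is small. About 50 participants are treated, only the women of childbearing potential among them are concerned, and they must be using contraception. The documents give no basis for an expected number of pregnancies. Neither the primary activation analysis nor the prediction aim is affected. This is a correction to safety-data wording that should be made, and it does not threaten the study's conclusions.

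**What to change.** 1. Reconcile the contraception text (Exclusion Criteria, Protection Against Risks), the AE and SAE reporting sections and the safety-data appendix, so that the period for reporting pregnancy matches whichever contraception period the sponsor keeps. State how a pregnancy in that period is expected to become known to the study.
2. State that pregnancy outcomes and congenital anomalies are not subject to the 8-week SAE cut-off.
3. Reconcile Table 1, the Run in Phase section and Protection Against Risks on the pre-run-in pregnancy test.
4. Check that the consent form and the Research Agreement agree with the result.

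No particular contraception period, test schedule or visit rule is proposed; those are for the sponsor and investigators. The cost is a protocol amendment and possibly a slightly later close-out of safety data for women of childbearing potential.
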